7.6.2 Pharmacokinetic/Pharmacodynamic endpoints

Descriptive statistics of plasma concentrations, ADA, PK and PD endpoints will be done by [REDACTED] and will be presented in Section 15.6,15.7 and 15.8 of the CTR.

The analysis of PK & PD parameters as well as the tables and graphs for the pharmacokinetic non-compartmental analyses will follow specific definitions of this TSAP or, otherwise, the BI standard procedure “Standards and processes for analyses performed within Clinical Pharmacokinetics/Pharmacodynamics” [001-MCS-36-472] (4).

7.7 EXTENT OF EXPOSURE

Descriptive statistics are planned for this section of the report based on the TS. The date and time of drug administration will be listed for each patient.

7.8 SAFETY ANALYSIS

All safety analyses will be performed on the TS.

If not stated otherwise, the safety results will be sorted by dose group/cohort.

The safety data for treated patients who failed to complete the study (dropouts or withdrawals) will be reported as far as their data are available. All withdrawals will be documented and the reason for withdrawal recorded.

7.8.1 Adverse Events

AEs will be coded with the most recent version of MedDRA. The version to be used will be specified in RPM and will be displayed as a footnote in the respective output.

The analyses of AEs will be descriptive in nature and will be based on BI standards as presented in “Analysis and Presentation of Adverse Event Data from Clinical Trials – Display Template” [BI-KMED-BDS-HTG-0041] (7) and [BI-KMED-BDS-HTG-0066] (2).

All analyses of AEs will be based on the number of subjects with AEs and not on the number of AEs.

The analysis of AEs will be based on the concept of treatment emergent AEs. That means that all AEs occurring between start of treatment and the EOT visit will be assigned to the respective treatment. All AEs occurring before first drug intake will be assigned to ‘screening’. For details on the treatment definition, see [Section 6.1](#).

Section 5.2.8.1.4 of the CTP:

All AEs meeting the criteria for a dose limiting event as defined in Section 7.4.1 are defined as AESIs for SRD and MRD cohort 1.

For MRD cohorts 2 and 3, the AESIs are defined as following:

Ocular related events (applicable to MRD cohorts 2 & 3)

- *Intraocular inflammation events*
 - *Anterior chamber cells of grade 1+ according to the Standardization of Uveitis Nomenclature (SUN) working group (WG) grading scheme (see CTP Table 5.2.1: I)*

- *Sterile inflammation of the vitreous of 1+ according to the NEI Grading of vitreous haze (see CTP Table 5.2.8.1.4: 1)*
- *Signs of vascular occlusion and inflammation (vasculitis) in the retina, including peripheral retinal hemorrhages in the area supplied by the occluded vessel (hemorrhage of the macula would not be included as this is a sign of wAMD disease)*
- *Visual acuity decrease of more than 15 letters from the previous visit*
- *Persistent IOP over 30 mmHg for 3 days after study treatment is administered, despite rescue treatment*

Hepatic injury

A hepatic injury is defined by the following alterations of hepatic laboratory parameters:

- *an elevation of AST and/or ALT ≥ 3 -fold ULN combined with an elevation of total bilirubin ≥ 2 -fold ULN measured in the same blood draw sample, and/or*
- *aminotransferase (ALT, and/or AST) elevations ≥ 10 -fold ULN*

These lab findings constitute a hepatic injury alert and the patients showing these lab abnormalities need to be followed up according to the “DILI checklist” provided in the eDC system.

In case of clinical symptoms of hepatic injury (icterus, unexplained encephalopathy, unexplained coagulopathy, right upper quadrant abdominal pain, etc.) without lab results (ALT, AST, total bilirubin) available, the investigator should make sure these parameters are analysed, if necessary, in an unscheduled blood test. Should the results meet the criteria of hepatic injury alert, the procedures described in the DILI checklist should be followed.

According to ICH E3 ([15](#)), in addition to Deaths and serious adverse events, AEs classified as ‘other significant’ need to be listed in the clinical trial report. These will be any non-serious adverse event that led to an action taken with study drug (e.g., discontinuation or dose reduced or interrupted).

An overall summary of AEs (including number of patients with any AE, DLEs (applicable for SRD part and MRD part cohort 1 only), drug related AEs, procedure related AEs, ocular AEs, AESIs, serious AEs and drug related serious AEs) will be presented.

The frequency of patients with AEs will be summarized by treatment group/cohort, primary system organ class (SOC) and preferred term (PT). Separate tables will be provided for patients with ocular AEs, for patients with DLEs, for patients with serious AEs, for patients with drug-related AEs, for patients with drug-related serious adverse events, for patients with AESIs, for patients with drug-related AESIs and for patients with study procedure related AEs. In addition, the frequency of patients with AEs will be summarized by worst intensity, treatment group/cohort, SOC and PT.

The system organ classes will be sorted alphabetically, PTs will be sorted by frequency (within SOC).

In addition, frequencies of patients with non-serious AEs that have an incidence of $> 5\%$ for at least one treatment will be summarised by treatment, primary SOC and PT (both trial parts combined).

For disclosure of adverse events on EudraCT the following three entries will be created, combined for both trial parts:

- Adverse Events per arm for disclosure on EudraCT
- Non-serious Adverse Events for disclosure on EudraCT
- Serious Adverse Events for disclosure on EudraCT

For all ocular adverse events, ocular symptoms will be listed in addition.

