#### 2.1.2 Primary endpoint(s)

SRD part:

- Number of patients with ocular dose limiting events (DLEs) from drug administration until end of trial (EOT). For definition of DLEs, refer to [Section 5.2.1](#).

MRD part:

- Number of patients with drug related AEs from drug administration until EOT.

[figure not shown]

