### **7.3.4 Safety analyses**

AEs will be coded using the Medical Dictionary for Drug Regulatory Activities (MedDRA). Standard BI summary tables and listings will be produced. For BI 836880, the residual effect period (REP) after IVT administration is not known. Therefore, all AEs with an onset between start of treatment and the respective EOT visit will be assigned to the on-treatment period for evaluation. The safety analysis will be performed by ‘treatment at onset’.

All treated patients will be included in the safety analysis. In general, safety analyses will be descriptive in nature and will be based on BI standards. No hypothesis testing is planned.

Statistical analysis and reporting of AEs will concentrate on treatment-emergent AEs, i.e. all AEs occurring between start of treatment and the EOT visit. AEs that start before first drug intake and deteriorate under treatment will also be considered as ‘treatment-emergent’.

Frequency, severity, and causal relationship of AEs will be tabulated by system organ class and preferred term after coding according to the current version of the MedDRA at the database lock.

Laboratory data will be analysed both quantitatively as well as qualitatively. The latter will be done via comparison of laboratory data to their reference ranges. Values outside the reference range as well as values defined as clinically relevant will be summarised. Treatment groups will be compared descriptively with regard to distribution parameters as well as with regard to frequency and percentage of patients with abnormal values or clinically relevant abnormal values.

Vital signs, physical examinations, or other safety-relevant data observed at screening, baseline, during the course of the trial and at the end-of-trial evaluation will be assessed with regard to possible changes compared to findings before start of treatment.

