4. CHANGES IN THE PLANNED ANALYSIS OF THE STUDY

All analyses as planned in CTP will be performed and are described in more detail in this TSAP.

The baseline definition of CTP was clarified in TSAP:

In CTP Section 5.1 it is '*For the endpoints, baseline is defined as the value at Visit 2; if not measured at Visit 2 then baseline is the value at Visit 1*'. If an actual time is given in the data, it will be checked whether the measurement at visit 2 was done before or after trial drug administration. If it is done after administration, the measurement will not be used as a baseline measurement. The baseline definition was updated to 'The baseline value is defined as the last measurement before first administration of BI 836880 (= value at V2, in case no actual time is given in data)'.

The definition of responder in further endpoints was clarified in TSAP. In CTP section 2.2.2, one of the further endpoints in MRD part is "Responder (yes/no) defined as absence of intra-retinal or sub-retinal fluid (IRF/SRF) or resolution of SHRM/PED in the study eye at Week 16 (Visit 6, cohort 3 only)". This definition is modified as: "Responder (yes/no) defined as resolution of IRF and SRF or resolution of SHRM/PED in the study eye at Week 16 (Visit 6, cohort 3 only)". To avoid redundancy, endpoint "Absence (yes/no) of intra-retinal or sub-retinal fluid (IRF, SRF) in the study eye at Week 16 (Visit 6, cohort 3 only)" and "Resolution (yes/no) of subretinal hyper-reflective material/retinal pigment epithelial detachment (SHRM/PED) in the study eye at Week 16 (Visit 6, cohort 3 only)" could be removed.

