6. GENERAL ANALYSIS DEFINITIONS

6.1 TREATMENTS

For basic study information on treatments to be administered, assignment of dose groups, selection of doses, refer to CTP Sections 3 and 4.

The trial will consist of an SRD part followed by an MRD part. Both parts will be conducted open-label, non-randomized, and uncontrolled.

It was planned to assign up to 42 patients in total, up to 15 in the SRD part (5 sequential dose groups comprising 3 patients each) and 27 in the MRD part (11 patients in dose group 1 (first cohort) and 16 patients in dose group 2 (4 patients from cohort 2 and 12 patients from cohort 3)).

For details of dosage and formulation see Tables 6.1:1 and 6.1:2 below.

Table 6.1: 1 Treatments and labels used in the analysis – SRD part

| Dose group | Treatment | | Short Label |
|------------|-----------|--|-------------|
| 1 | A | BI 836880, 80 mg/mL solution, 0.06 mg, ivt | BI 0.06mg |
| 2 | B | BI 836880, 80 mg/mL solution, 0.18 mg, ivt | BI 0.18mg |
| 3 | C | BI 836880, 80 mg/mL solution, 0.5 mg, ivt | BI 0.5mg |
| 4 | D | BI 836880, 80 mg/mL solution, 1.0 mg, ivt | BI 1mg |
| 5 | E | BI 836880, 80 mg/mL solution, 2.0 mg, ivt | BI 2mg |

Table 6.1: 2 Treatments and labels used in the analysis – MRD part

| Dose group | Treatment | | Short Label* |
|------------|-----------|---|-----------------------|
| 1 | F | BI 836880 Concentrate for Solution for Injection 80 mg/mL, diluted with Diluent to 20 mg/mL solution, 1.0 mg, ivt | BI 1mg q4w – cohort 1 |
| 2 | G | BI 836880 Concentrate for Solution for Injection 80 mg/mL, diluted with Diluent to 40 mg/mL solution, 2.0 mg, ivt | BI 1mg q4w – cohort 2 |
| 3 | H | BI 836880 solution for injection 40 mg/mL, 2.0 mg, ivt | BI 1mg q4w – cohort 3 |

* cohort 1: resistant patients, cohort 2: naïve patients, cohort 3; frequently treated patients

Cohorts 2 and 3 are displayed separately although belonging to the same dose group.

Section 7.3.4 of the CTP:

For BI 836880, the residual effect period (REP) after IVT administration is not known. Therefore, all AEs with an onset between start of treatment and the respective EOT visit will be assigned to the on-treatment period for evaluation.

Thus, no follow-up period is considered in this trial. The following separate study phases will be defined for the analyses of AEs:

- **Screening** (ranging from 0:00h (midnight) on the day of informed consent until the first administration time of BI 836880)
- **On treatment**

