 - **BI treatment** (separately for each treatment, ranging from the time of first administration of BI 836880 until 0:00h (midnight) on the day after trial completion date) – labelled with the short labels defined in tables above

The following AE displays will be provided in the report:

Section 15.3 and Appendix 16.1.13.1.8 (for ClinicalTrials.gov and EudraCT) of the CTR displays:

In these displays, the on-treatment phase will be analysed (labelled with the short label of the study treatment - the actual treatment is equal to the study treatment). Screening will not be included in this analysis. In Section 15.3, a total overall, on treatment phases included in this analysis ("Total") will be provided in addition.

In Section 15.4 and Appendix 16.2 (Listings) of the CTR displays, the screening period will be included, and no totals will be provided.

Tables of vital signs and laboratory values will present results for the above mentioned on treatment phase.

For detailed information on the handling of the treatments refer to the Technical TSAP ADS (analysis data set) plan and the Analysis Data Reviewers guide.

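### The SAP assigns every AE with onset before first dose to screening, although the protocol counts those that deteriorate under treatment as treatment-emergent

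*SAP*

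**What the plan says.** Protocol 7.3.4 centres AE reporting on treatment-emergent events. It takes those with onset from start of treatment to the EOT visit, and then adds a second class: "AEs that start before first drug intake and deteriorate under treatment will also be considered as" treatment-emergent.

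SAP 7.8.1 says that it follows the treatment-emergent concept, but gives only two assignments. For the on-treatment phase, "all AEs occurring between start of treatment and the EOT visit will be assigned to the respective treatment". For the rest, "All AEs occurring before first drug intake will be assigned to" screening. The deterioration class does not appear.

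SAP 6.1 works the same way. It repeats the protocol's onset sentence ("all AEs with an onset between start of treatment and the respective EOT visit will be assigned to the on-treatment period for evaluation") without the deterioration sentence, and defines screening as "ranging from 0:00h (midnight) on the day of informed consent until the first administration time of BI 836880". For CTR Section 15.3 and the ClinicalTrials.gov and EudraCT displays it adds: "Screening will not be included in this analysis". Screening AEs appear only in Section 15.4 and the Appendix 16.2 listings, which carry no totals.

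SAP 4 opens with "All analyses as planned in CTP will be performed and are described in more detail in this TSAP". It then declares two items, the baseline definition and the responder definition. AE phasing is not among them.

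**The concern.** The two current texts give different counts for the same patient. Take an event that starts after consent, is still present at the first injection and then becomes worse. Under the protocol it is treatment-emergent. Under the SAP it belongs to screening and is absent from every AE summary table.

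The rule feeds the AE endpoints: study-eye ocular AEs (secondary in both parts), drug-related AEs in the SRD part (secondary), and the MRD primary endpoint, "Number of patients with drug related AEs from drug administration until EOT". It also feeds the AESI, serious-AE and worst-intensity tables. Leaving out a class of events can lower these counts or leave them unchanged; it cannot raise them. In a safety trial with cohorts of 4 to 12 patients, a one-sided rule of this kind should be intended and declared.

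**Working it through.** The plan gives no figure to reproduce, because no rate of such events is stated. The check is a comparison of texts, followed by a scale calculation.

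1. **Can such events exist in the data?** Yes. Protocol 5.2.8.2.1 collects all AEs from signing of consent. Screening lasts 3 to 42 days in the SRD part (Flow Chart I). In the MRD part it is Day -14 ±10 (Flow Charts II to IV), that is Day -24 to Day -4. SAP Table 6.7: 1 gives Day -28 to -3.

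2. **How does each document treat three cases?**
   - Onset after first dose: on treatment in both.
   - Onset before first dose, no worsening: not treatment-emergent in either.
   - Onset before first dose, worsening after it, kept as one record: treatment-emergent under protocol 7.3.4, screening under SAP 7.8.1 and 6.1. Only this case differs.

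3. **Is worsening re-recorded anyway?** Often.
   - Protocol 5.1 has clinically significant worsening in the efficacy assessments reported as an AE.
   - Protocol 5.2.8.2.3 has worsening of the underlying disease or of pre-existing conditions recorded as an AE.
   - Clinically significant slit-lamp findings at Visit 1 (6.2.1.1, 6.2.2.1) and relevant screening ECG findings (5.2.6) are baseline conditions, so their worsening falls under 5.2.8.2.3.
   - What remains is an AE that arises between consent and first dose, is not a baseline condition, worsens, and keeps its original onset date. Neither document says that such an event gets a new record.

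4. **When does a count change?** AE analyses are per subject (SAP 7.8.1). The overall or study-eye ocular count changes if the patient has no other on-treatment AE of that type; relatedness is not needed. The drug-related count changes only if the event is judged drug related and the patient has no other on-treatment drug-related AE.

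5. **Scale of one missed patient** (100/n percentage points; cohort sizes from SAP 6.1):
   - MRD cohort 1: 100/11 = 9.1
   - MRD cohort 2: 100/4 = 25.0
   - MRD cohort 3: 100/12 = 8.3
   - MRD total: 100/27 = 3.7
   - SRD total: 100/15 = 6.7

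6. **Chance of at least one missed patient among 27**, 1 − (1 − q)^27, where q is an assumed per-patient probability that is not in the documents: q = 1% gives 24%, q = 5% gives 75%, q = 10% gives 94%. The range is wide because q is unknown. It shows sensitivity and is not a forecast.

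**The case against.** The strongest reply is that little is lost in practice. Much ocular worsening reaches the database as a new AE or as worsening of a baseline condition (step 3). The protocol's causality guidance (5.2.8.1.6) names pre-treatment cases as an argument against a drug relationship, so a record that keeps a pre-dose onset is unlikely to be judged related. If the investigator does blame the drug for the worsening, a new post-dose record is the natural entry, and the SAP counts it. Screening AEs also stay visible in the listings, no hypothesis is tested, and there is no comparator arm. All of this stands, and it limits the reach to the drug-related counts in particular.

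It can also be said that protocol 7.3.4 itself contains the onset rule and analyses safety by treatment at onset, so that the SAP merely paraphrases it incompletely. That may well be the origin. But the protocol adds the deterioration class in the same section, and the SAP's wording excludes it by covering all pre-dose AEs.

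Lastly, the SAP defers detail to sponsor AE standards and to an analysis-dataset plan that are not available here. These may contain the missing rule, but they cannot be assumed to override explicit SAP text.

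Two stronger readings are tempting. One is that the MRD primary endpoint will be undercounted; the documents do not show this, because both conditions in step 4 must hold and no frequency is given. The other is that SAP 4 claims no changes at all; it declares two, and simply omits this one.

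**Conclusion.** The SAP rule conflicts with protocol 7.3.4 and the conflict is undeclared. As written, the treatment-emergent tables omit AEs that start between consent and first dose, worsen after dosing and are not re-recorded. The effect falls mainly on the overall and study-eye ocular counts, and on the drug-related counts only under the conditions in step 4. Its direction is fixed: counts can only be too low. Its frequency is unknown and probably small, but with these cohort sizes one patient is a visible share. The conclusion assumes that the SAP text is applied literally and that at least some worsening events keep their original onset date. Whether any patient is actually affected cannot be determined from the documents. Because all analyses are descriptive, no test or error rate is involved.

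**What to change.** Add the deterioration rule of protocol 7.3.4 to SAP 7.8.1 and to the phase definitions in SAP 6.1: an AE with onset before first dose that deteriorates under treatment goes to the on-treatment phase, and all other pre-dose AEs stay in screening.

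State how deterioration is identified in the collected data, either as a new record with a post-dose onset or as a recorded change within the existing event. The protocol gives no measure of deterioration, so the SAP has to name one. If the onset-only rule is intended, list it in SAP 4 with a reason instead.

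The cost is one sentence and a small derivation. If the AE data hold no dated change within an event, a manual review of the few screening-onset AEs serves the same purpose.

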The following safety measures have been implemented to mitigate the risk and ensure early detection of intraocular inflammation (IOI): fluorescein angiography (FA) imaging will be required at screening and wide-angle fundus photography with a vitreous haze assessment will be required at every visit. Reports of IOI will be treated as an AE of special interest (AESI), see also [Section 5.2.8.1.4](#).

Furthermore, although rare, a potential for drug-induced liver injury (DILI) is under constant surveillance by sponsors and regulators. Therefore, this trial requires timely detection, evaluation, and follow-up of laboratory alterations in selected liver laboratory parameters to ensure patients' safety, see also [Section 5.2.8.1.4](#), AESIs. The implications of the current Coronavirus Disease 2019 (COVID-19) pandemic are summarized in [Section 10.4](#).

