## 5.2 ASSESSMENT OF SAFETY

### 5.2.1 Dose limiting event

For the SRD part and MRD cohort 1:

A DLE is defined as the occurrence of any of the following events in the study eye:

- Development of sterile endophthalmitis and/or sterile inflammation of the vitreous grade 4+ according to standardization of Uveitis Nomenclature (SUN) working group (WG) grading scheme for anterior chamber cells (see [Table 5.2.1: 1](#)) and a duration of 5 or more days between day 1 and day 8
- Visual decrease of more than 15 letters at any given timepoint
- Persistent IOP over 30 mmHg for 3 days
- Signs of vascular occlusion in a 1st (the main branch) or 2nd degree (the vessel after the first bifurcation of the main branch) retinal vessel, including peripheral retinal hemorrhages in the area supplied by the occluded vessel (hemorrhage of the macula would not be included as this is a symptom of the disease).

Table 5.2.1: 1 The SUN Working Group Grading Scheme for Anterior Chamber Cells [[R18-1136](#)]

Grade	Cells in Field 
0	<1
0.5+	1-5
1+	6-15
2+	16-25
3+	26-50
4+	>50

 Field size is a 1 mm by 1 mm slit beam.

DLE criteria are not applicable to MRD cohorts 2 and 3. Should an event involving intraocular inflammation/signs of vascular occlusion, decreases in visual acuity, and/or intraocular pressure occur, the event should only be reported as an AESI as described in [Section 5.2.8.1](#), and not as a DLE.

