#### 5.2.8.1.4 Adverse events of special interest (AESIs)

The term AESI relates to any specific AE that has been identified at the project level as being of particular concern for prospective safety monitoring and safety assessment within this trial, e.g. the potential for AEs based on knowledge from other compounds in the same class.

AESIs need to be reported to the sponsor’s Pharmacovigilance Department within the same timeframe that applies to SAEs, please see above.

The following are considered as AESIs:

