##### **Ocular related events** (applicable to MRD cohorts 2 & 3)

- Intraocular inflammation events
  - ⊖ Anterior chamber cells of grade 1+ according to the Standardization of Uveitis Nomenclature (SUN) working group (WG) grading scheme (see [Table 5.2.1: 1](#))
  - ⊖ Sterile inflammation of the vitreous of 1+ according to the NEI Grading of vitreous haze (see [Table 5.2.8.1.4: 1](#) below)
- Signs of vascular occlusion and inflammation (vasculitis) in the retina, including peripheral retinal hemorrhages in the area supplied by the occluded vessel (hemorrhage of the macula would not be included as this is a sign of wAMD disease)
- Visual acuity decrease of more than 15 letters from the previous visit

Proprietary confidential information © 2022 Boehringer Ingelheim International GmbH or one or more of its affiliated companies

- Persistent IOP over 30 mmHg for 3 days after study treatment is administered, despite rescue treatment

Table 5.2.8.1.4: 1 The NEI Grading Scale of Vitreous Haze [[R22-2854](#)]

Scale	Description	Clinical findings
0	Nil	None
0.5+	Trace	
1+	Minimal	Posterior pole clearly visible
2+	Mild	Posterior pole details slightly hazy
3+	Moderate	Posterior pole details very hazy
4+	Marked	Posterior pole details barely visible
5+	Severe	Fundal details not visible

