### **Hepatic injury**

A hepatic injury is defined by the following alterations of hepatic laboratory parameters:

- an elevation of AST and/or ALT  $\geq$  3 fold ULN combined with an elevation of total bilirubin  $\geq$  2 fold ULN measured in the same blood draw sample, and/or
- aminotransferase (ALT, and/or AST) elevations  $\geq$  10 fold ULN

These lab findings constitute a hepatic injury alert and the patients showing these lab abnormalities need to be followed up according to the “DILI checklist” provided in the eDC system.

In case of clinical symptoms of hepatic injury (icterus, unexplained encephalopathy, unexplained coagulopathy, right upper quadrant abdominal pain, etc.) without lab results (ALT, AST, total bilirubin) available, the investigator should make sure these parameters are analysed, if necessary in an unscheduled blood test. Should the results meet the criteria of hepatic injury alert, the procedures described in the DILI checklist should be followed.

All AEs meeting the criteria for a dose limiting event as defined in [Section 5.2.1](#) are defined as AESIs for this trial.

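### SAP 7.8.1 can be read to limit hepatic injury as an AESI to MRD cohorts 2 and 3, although the protocol sets no cohort limit; the practical exposure is MRD cohort 1

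*SAP*

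**What the plan says.** **Protocol.** Section 5.2.8.1.4 opens its list with "The following are considered as AESIs" and names no cohort. Two headings follow. The ocular heading carries a limit, "applicable to MRD cohorts 2 & 3". The hepatic heading carries none and begins "A hepatic injury is defined by the following alterations of hepatic laboratory parameters". A closing sentence makes events that meet the DLE criteria AESIs for the trial. Section 1.4 presents liver surveillance as a requirement of the whole trial: "this trial requires timely detection, evaluation, and follow-up of laboratory alterations in selected liver laboratory parameters". It then points to the AESI section. Section 5.2.5 refers to the hepatic injury criteria when it describes the safety laboratory tests scheduled in all four flow charts.

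**SAP.** Section 7.8.1 gives its text as Section 5.2.8.1.4 of the protocol, but arranges it differently. It starts with the DLE sentence: "All AEs meeting the criteria for a dose limiting event as defined in Section 7.4.1 are defined as AESIs for SRD and MRD cohort 1". It then inserts "For MRD cohorts 2 and 3, the AESIs are defined as following", and after that come the ocular events and hepatic injury. The same section plans an AESI entry in the overall AE summary, a table of patients with AESIs and a table of patients with drug-related AESIs. SAP Section 4 says that the analyses planned in the protocol will be carried out. It describes clarifications of the baseline and responder definitions only.

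**The concern.** The SAP is the document from which tables are programmed. Taken literally, 7.8.1 gives one AESI definition to the SRD part and MRD cohort 1 (DLE criteria) and another to cohorts 2 and 3 (ocular events plus hepatic injury). On that reading a hepatic injury in cohort 1 would not count as an AESI, while the same event in cohort 2 or 3 would. SAP Section 7 puts the three MRD cohorts in one table, so a single AESI row could carry different hepatic definitions from column to column with nothing to tell the reader.

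The primary endpoints of both trial parts are safety counts, so the safety definitions should match the protocol or depart from it openly.

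**Working it through.** The plan gives no figure to reproduce. The check sets the texts side by side and then counts patients.

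**1. Scope of each AESI group**

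| AESI group | Protocol 5.2.8.1.4 | SAP 7.8.1, read literally |
|---|---|---|
| DLE-criteria events | the trial | SRD and MRD cohort 1 |
| Ocular events | MRD cohorts 2 and 3 | MRD cohorts 2 and 3 |
| Hepatic injury | no cohort limit | MRD cohorts 2 and 3 |

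The first row also differs, but protocol 5.2.1 supports the narrower SAP scope: it says that the DLE criteria do not apply to MRD cohorts 2 and 3. No comparable protocol text supports the narrower scope in the hepatic row.

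**2. Can hepatic injury enter through the DLE criteria?** Protocol 5.2.1 introduces them with "A DLE is defined as the occurrence of any of the following events in the study eye". They cover ocular inflammation, loss of letters, raised intraocular pressure and retinal vascular occlusion. None is hepatic, so under the SAP definition this route is closed for SRD and cohort 1.

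**3. Is the difference declared?** SAP Section 4 does not mention AESIs.

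**4. Patients by part** (SAP 6.1): SRD 15, MRD cohort 1 11, cohort 2 4, cohort 3 12; total 15 + 11 + 4 + 12 = 42.

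- Inside the SAP's literal hepatic scope: 4 + 12 = 16.
- Outside it: 15 + 11 = 26, and 26/42 = 61.9%.

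**5. Which of the 26 are realistically exposed?** Protocol 1.2 reports that the SRD part was complete at the 25 March 2022 cut-off, with all 15 patients followed to the end-of-trial visit. The 6 AEs after dosing were all eye disorders. No hepatic AE was reported there, so there is no reported SRD hepatic AESI to omit. That leaves MRD cohort 1: 26 − 15 = 11 planned patients. The visible text does not show whether a hepatic injury occurred among them. One case would be 1/11 = 9.1% of the cohort.

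**The case against.** The strongest reply is that the restrictive reading is not the only one. In SAP 7.8.1 the ocular heading repeats its own limit to cohorts 2 and 3, and the hepatic heading has none. If the lead-in governed both lists, that repeated limit would be redundant. The block is also labelled as protocol text, so a programmer who resolves the doubt by the protocol would apply hepatic injury to everyone. This stands as a plausible account of intent. It does not remove the problem, because the inserted lead-in then contradicts the intent.

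Second, investigators record and report AESIs under the protocol definition (5.2.8.2.1 and 5.2.8.2.2). If the tables use that reported classification, nothing is omitted. This also stands. The visible SAP gives a definition and does not say which source the tables use, so omission is possible and not established.

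Third, no safety data would be lost. A hepatic injury reported as an AE would still appear in the general AE tables and, where applicable, in the drug-related table that carries the MRD primary endpoint and in the serious AE tables. Abnormal laboratory values are tabulated and flagged under SAP 7.8.2. The follow-up of hepatic injury alerts comes from the protocol and does not depend on the SAP. All of this is correct, and it confines the effect to one summary row and two descriptive tables.

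A reader might infer that the AESI tables will omit hepatic injury for 26 of 42 patients (62%), or that a missed case would be one third of an SRD dose group. The documents do not support either inference. The omission depends on how the tables are programmed, and the SRD part had finished with only eye-disorder AEs.

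**Conclusion.** The conflict is real. SAP 7.8.1 attributes to the protocol a cohort restriction on hepatic injury that the protocol does not contain, and SAP Section 4 does not declare it. At best the text is ambiguous; at worst it gives cohorts shown in the same table different AESI definitions.

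The consequence is limited and conditional. If the three AESI displays are programmed from the SAP text, a hepatic injury in MRD cohort 1 (11 planned patients, 9% per case) could be left out of them. This rests on two assumptions: that the tables follow the SAP wording and not an investigator-reported AESI classification, and that the SRD adverse events described in protocol 1.2 are complete. No endpoint changes and no hypothesis test is affected. The point is worth correcting because it concerns a stated safety definition and the correction is simple.

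**What to change.** Reword the AESI definition in SAP 7.8.1 to say that:

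- hepatic injury, as defined in protocol 5.2.8.1.4, is an AESI for the SRD part and for all MRD cohorts;
- events meeting the DLE criteria are, in addition, AESIs for the SRD part and MRD cohort 1;
- the listed ocular events are AESIs for MRD cohorts 2 and 3.

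If the sponsor did intend to restrict hepatic injury to cohorts 2 and 3, SAP Section 4 should declare and justify that as a change from the protocol.

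The cost is a short rewording and a check that the programming of the three AESI displays agrees with it. No new data are needed and trial conduct does not change. A separate derivation of hepatic injury from the laboratory data is not needed to resolve the discrepancy.
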